### 5.6 Dose Modification

Subjects will be asked to maintain the full dose throughout the treatment period. However, should some toxicity appear, dose modification will be applied and recorded.

Toxicity will be evaluated at each visit using the most recent version of the NCI terminology criteria (CTCAE version 4.0.3, published 06/14/2010).

If grade 1 toxicity occurs, the patient will be maintained on full dose. Toxicity will be checked depending on clinical relevance.

In case of grade 2 toxicity or higher, the dose will be changed according to the potential relationship to study drug as listed in the table below.

Toxicity	Attribution to study drug				
Grade	Unrelated	Unlikely	Possible	Probable	Definite
1	C	C	C	C	C
2	C	C	S-R 	S-R 	S-R 
3	S-R 	S-R 	S-R 	W	W
4	S-R 	S-R 	W	W	W

C = Continue drug

S-R^0 = Stop drug until toxicity reaches grade 1 or lower, then restart drug at full dose (100 mg/day). If toxicity resumes, stop drug again until toxicity reaches grade 1 or lower, and then restart at alternate day and maintain the reduced dose.

S-R^1 = Stop drug until toxicity reaches grade 1 or lower, then reduce drug by 50% (100 mg at alternate day) and maintain the reduced dose.

[figure not shown]
S-R^2 = Stop drug until toxicity reaches grade 1 or lower, then reduce drug by 50% (100 mg at alternate day) for 1 month. If toxicity is no more than grade 1, restart drug at full dose (100 mg/day). If toxicity resumes after reintroduction of full dose, stop drug again until toxicity reaches grade 1 or lower and then reduce drug by 50% (100 mg at alternate day) and maintain this dose. No further reductions will be permitted and patients with returning toxicities will be removed from the study.

W = Withdrawal

For dyspepsia and GERD management only, a PPI1) will be added.

In case of dyspepsia grade 1 (G1), PPI will be added for two weeks. If remission, PPI will be stopped. If symptom persists or recurs, it will be defined as  $\geq$  grade 2 (G2).

In case of dyspepsia  $\geq$  G2, the symptom will be managed as follows:

The clinical investigators of the study may be helped in their decisions by consultation of other specialists (Gastroenterologist).

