## 4.2 Exclusion Criteria

4.2.1 Subjects with chronic treatment (at least twice/week for more than 3 months) with Aspirin or other NSAIDs.

4.2.2 History of allergic reactions attributed to compounds of similar chemical or biological composition to aspirin, NSAIDs, COX2 inhibitors.

4.2.3 Invasive malignancy (with the exclusion of basal cell carcinoma or skin squamous cell carcinoma) diagnosed during the last 2 years before randomization; stage I-II invasive malignancies that were diagnosed more than 2 years prior to randomization and have been treated curatively are allowed as long as all treatment is finished at least 18 months prior to randomization.

4.2.4 History of therapeutic doses of anticoagulants including warfarin and low molecular weight Heparin (e.g. for prior deep venous thrombosis and pulmonary embolisms) in the preceding year.

4.2.5 Uncontrolled intercurrent illness including, but not limited to, ongoing or active infection, symptomatic congestive heart failure, unstable angina pectoris, cardiac arrhythmia, or psychiatric illness/social situations that would limit compliance with study requirements.

4.2.6 Pregnant women are excluded from this study because Aspirin is an agent with the potential for teratogenic or abortifacient effects. Because there is an unknown but potential risk for adverse events in nursing infants secondary to treatment of the mother with Aspirin, breastfeeding should be discontinued if the mother is treated with Aspirin.

4.2.7 Individual may not be receiving any other investigational agents, antiplatelet agents (e.g. aspirin, clopidogrel (plavix or others)), anticoagulants (e.g. heparin or heparinoids, coumadin, or others), metotrexate, lithium.

4.2.8 Participants with bleeding diathesis, history of gastric/duodenal ulcers in the last 5 years, NSAID-precipitated bronchospasm, patients unwilling or unable to limit alcohol consumption to i.e.  $\leq 3$  alcohol drinks a day.

4.2.9 Participants who in the opinion of the PI will be at higher risk of ASA-related complications.

4.2.10 Participants with known inability to adequately absorb oral medication.

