### 5.4 Contraindications

Aspirin should not be taken by people who are allergic to ibuprofen or naproxen, or who have salicylate intolerance or a more generalized drug intolerance to non-steroidal anti-inflammatory drugs (NSAIDs), and caution should be exercised in those with asthma or NSAID-precipitated bronchospasm. Owing to its effect on the stomach lining, manufacturers recommend people with peptic ulcers, mild diabetes, or gastritis seek medical advice before using aspirin. Even if none of these conditions is present, the risk of stomach bleeding is still increased when aspirin is taken with alcohol or warfarin. Patients with hemophilia or other bleeding tendencies should not take aspirin or other salicylates. Aspirin is known to cause haemolytic anemia in people who have the genetic disease glucose-6-phosphate dehydrogenase deficiency, particularly in large doses and depending on the severity of the disease. People with kidney disease, hyperuricemia, or gout should not take aspirin because it inhibits the kidneys' ability to excrete uric acid, and thus may exacerbate these conditions.

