### 6.2 Reported Adverse Events and Potential Risks

Potential risks and rare side effects related to the treatment can be summarized in the following four major categories:

- Upset stomach and heartburn.
- Easy bruising/bleeding, difficulty hearing, ringing in the ears, change in the amount of urine, persistent or severe nausea/vomiting, unexplained tiredness, dizziness, dark urine, yellowing eyes/skin.
- Black/tarry stools, persistent or severe stomach/abdominal pain, vomit that looks like coffee grounds, slurred speech, weakness on one side of the body, sudden vision changes or severe headache.
- Rash, itching/swelling (especially of the face/tongue/throat), severe dizziness, trouble breathing.

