#### CTCAE v4.0 general severity guidelines:

Grade	Severity	Description
1	Mild	Mild; asymptomatic or mild symptoms; clinical or diagnostic observations only; intervention not indicated.
2	Moderate	Moderate; minimal, local or noninvasive intervention indicated; limiting age-appropriate instrumental activities of daily living (ADL)*.
3	Severe	Severe or medically significant but not immediately life-threatening; hospitalization or prolongation of hospitalization indicated; disabling; limiting self-care ADL**.
4	Life-threatening	Life-threatening consequences; urgent intervention indicated.

5	Fatal	Death related to AE.
---	-------	----------------------

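### Section 5.6 has no event-specific mandatory stop for drug-related hypersensitivity or bronchospasm below grade 3 probable, so reactions that would bar entry to the trial are followed by a restart

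*Combined protocol and SAP*

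**What the plan says.** Section 5.6 makes dose modification a rule, not advice: "In case of grade 2 toxicity or higher, the dose will be changed according to the potential relationship to study drug". Event type does not enter. Two of its restart codes matter here.

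- **S-R0** (grade 2, possible or probable): hold until grade 1 or lower, then restart at 100 mg/day. On recurrence: "If toxicity resumes, stop drug again until toxicity reaches grade 1 or lower, and then restart at alternate day and maintain the reduced dose".
- **S-R1** (grade 2 definite; grade 3 possible): hold until grade 1 or lower, "then reduce drug by 50% (100 mg at alternate day) and maintain the reduced dose".

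Grade 3 probable or definite, and grade 4 possible, probable or definite, are coded W (withdrawal). The only event-specific handling visible in 5.6 is for dyspepsia and GERD.

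Elsewhere, 6.2 lists among the potential risks of treatment: "Rash, itching/swelling (especially of the face/tongue/throat), severe dizziness, trouble breathing". Exclusion 4.2.2 reads: "History of allergic reactions attributed to compounds of similar chemical or biological composition to aspirin, NSAIDs, COX2 inhibitors". Exclusion 4.2.8 adds NSAID-precipitated bronchospasm. Section 5.4 says: "Aspirin should not be taken by people who are allergic to ibuprofen or naproxen, or who have salicylate intolerance", and extends this to wider NSAID intolerance; for asthma or NSAID-precipitated bronchospasm it asks only for caution. Sections 8.3 and 8.4 list adverse events and medical contraindication as reasons for which a participant may stop agent or leave the study.

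**The concern.** The protocol foresees allergic and respiratory reactions to the agent (6.2) and treats a history of them as disqualifying (4.2.2, 4.2.8). A participant who has a first such reaction on study acquires the history that would have barred entry. For part of the grade and attribution range, 5.6 then directs that blinded drug be given again. Under S-R0 it does so a second time after a recurrence.

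For a participant on aspirin whose reaction is genuine, the written rule is re-exposure to the suspected cause. No supervised restart is described, and scheduled contacts after month 1 fall at months 3, 6, 9, 12 and 13, so most are two to three months apart. These are asymptomatic volunteers in a prevention trial, which leaves little reason to accept that exposure. Avoiding it depends on the investigator choosing a permissive exit over a directive table.

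**Working it through.** **Step 1: read the related cells of the 5.6 table.** Inputs are the table and its key.

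| Grade | Possible | Probable | Definite |
|---|---|---|---|
| 2 | S-R0 (restart, full dose) | S-R0 (restart, full dose) | S-R1 (restart, alternate days) |
| 3 | S-R1 (restart, alternate days) | W | W |
| 4 | W | W | W |

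Restart: 3 + 1 + 0 = 4 of 9 cells. Withdrawal: 0 + 2 + 3 = 5 of 9. Grade 1 continues at full dose whatever the attribution.

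**Step 2: set those cells beside the other sections.**

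- 4.2.2 has no severity floor and no reduced-dose exception. A prior grade 2 allergic reaction attributed to an NSAID excludes; the same reaction on study, judged definitely related, is restarted on alternate days.
- 4.2.8 treats NSAID-precipitated bronchospasm in the same way.
- 5.4 advises against aspirin in salicylate or NSAID intolerance but is not written as an on-study stopping rule.
- 8.3 and 8.4 are permissive. Section 6.9 allows unblinding for unacceptable toxicity thought to be related to the agent, but a participant unblinded early is then taken off study.
- The sentence in 5.6 that removes patients with returning toxicities stands in the S-R2 definition, which covers unrelated and unlikely events. Read more widely, it would still act only after re-exposure.
- 5.5 shows that the protocol can write a mandatory stop: excess NSAID or glucocorticosteroid use ends study drug, while the participant stays for the yearly scan and the intent-to-treat analysis.

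**Step 3: how severe is what remains?** The general grade 2 description in 11.1.3 is "Moderate; minimal, local or noninvasive intervention indicated". The exposed range is that level, plus grade 3 events judged only possibly related.

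**Step 4: cell count after the fix.** Hypersensitivity: 4 restart cells become 0. Bronchospasm: 4 become 1 (grade 2 possible stays S-R0).

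**Step 5: what the fix could cost in power.** Inputs from 13.3: 64 per arm, difference 0.8 mm, SD 1.6 mm, two-sided alpha 0.05, two-sample t-test. The noncentrality is 0.8 / (1.6 × √(2/64)) = 2.83 on 126 df, giving 80.1% and reproducing the plan's 80%.

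Now assume that k of the 64 aspirin participants stop early and lose all benefit, with SD unchanged. The difference becomes 0.8 × (1 − k/64). If the restart would itself have kept only half the benefit, the loss due to the fix is half as large: 0.8 × (1 − 0.5k/64).

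| k (assumed) | Difference, all benefit lost | Power | Power, half lost |
|---|---|---|---|
| 0 | 0.800 mm | 80.1% | 80.1% |
| 1 | 0.788 mm | 78.9% | 79.5% |
| 2 | 0.775 mm | 77.6% | 78.9% |
| 3 | 0.763 mm | 76.3% | 78.3% |

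Neither k nor the retained share comes from the documents. The table measures a possible cost of the fix, not the harm that it prevents.

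**The case against.** The strongest reply is that the protocol already deals with this. Section 5.4 sits under agent administration, not among the entry criteria, and is not limited to pre-study history. A participant with a drug-related allergic reaction can fairly be read as someone who should not take aspirin, and 8.3 then offers an exit with follow-up continued. That stands in part: a careful investigator has a documented basis for stopping. It does not settle the matter, because 5.6 says what will be done, 8.3 says what may be done, and 5.4 asks only for caution over bronchospasm.

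Three further points stand. The remaining range is narrow: prior reactors are excluded, 4.2.9 lets the PI exclude people at higher risk of aspirin complications, and drug is held until grade 1 or lower before any restart. One figure in 5.6 is not visible in the copy reviewed; the text around it suggests the dyspepsia scheme, but that cannot be confirmed. Section 11 refers to the Investigator Brochure or package insert, which was not available and may carry its own instruction.

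A reader might infer that the plan has no mandatory stop at all for allergic reactions. It has: the five W cells apply to any toxicity. A reader might also infer that everyone restarted is an aspirin reactor. Attribution is made blind and half the participants take placebo, so some of these events will not be reactions to aspirin.

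**Conclusion.** The point holds in a limited form. In the visible text of 5.6, hypersensitivity and bronchospasm have no event-specific mandatory stop below grade 3 probable, and four of the nine related cells at grades 2 to 4 direct a restart. This fits poorly with 4.2.2, 4.2.8 and 5.4. It is a stated rule that is less safe if followed than the alternative, not merely a missing detail.

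It is a cheap improvement for patient safety. It does not threaten the validity of the trial, and the primary analysis is untouched by the gap. The number of participants affected and the harm avoided cannot be derived from the documents. Confidence is moderate, because of the unseen figure, the unavailable product information and the partial exit through 5.4 and 8.3.

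**What to change.** Add a footnote to the 5.6 table, for example: *Any allergic or hypersensitivity reaction of grade 2 or higher judged possibly, probably or definitely related, and any bronchospasm that is grade 2 or higher and probably or definitely related, or grade 3 and possibly related, leads to permanent discontinuation of study agent instead of S-R0 or S-R1. The participant stays on study and has the 12-month CT under 8.3.*

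Leaving grade 2, possibly related bronchospasm at S-R0 is a clinical judgement, in line with the softer wording of 5.4; the sponsor could reasonably choose the stricter cut-off.

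The cost is one protocol amendment. It uses the grade and attribution already recorded, needs no unblinding, and changes neither the analysis nor the sample size. The downside is that a few participants stop drug early, including some on placebo and some whose event was not caused by the drug. Under the assumed one to three aspirin participants, power falls to between 78.9% and 76.3% if all benefit is lost, or between 79.5% and 78.3% if the restart would have kept only half.

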## 5.7 Adherence/Compliance

Estimates for patient non-adherence to various medical regimens range from 20% to 100%, and some authorities have come to view the difficulty of guaranteeing patient adherence as one of the most serious problems facing medical practice today. Recent data from ongoing chemoprevention studies have estimated adherence to be between 60% and 100%. The disparity between the highest and lowest estimates may largely be attributed to methodology, given that the assessment of adherence remains problematic - there is as of yet no 'gold standard' to measure patient adherence. Because no such gauge exists, we propose the use of multiple methods of adherence monitoring: subject self-reporting, calendar completion and dose count.

Although drug concentration will not be measured in the blood, compliance will be monitored in the following ways:

***Patient Self-Report:*** The patient's history, the most direct source of information, is the most widely employed measure of a patient's adherence to their medical regimen. However, patient self-reporting has

been criticized as being too subjective, with patients tending to over-report their adherence by as much as two to fourfold. Positive information is helpful, but false negatives are common.

Calendar completion: Each subject will be provided a 7-month calendar as a reminder of drug intake (Appendix B). Each subject will be asked to cross the corresponding day of the calendar (1 cross for each tablet, i.e. 1 cross per day). Subjects are asked to fill the calendar and some additional space will be left for patient's notes. Each calendar will be returned at the next scheduled visit.

Dose count: Each subject will receive a 7-month supply of the drug or placebo and will be asked to return all full and empty bottles. Compliance will be measured as follows:  
number of tablets taken (i.e., number of tablets given-number of tablets returned)/number of tablets that should have been taken during that period of time.

In cases where the tablets are not returned, the compliance has to be calculated from the calendar.

Serum Thromboxane (TXB2): As an additional measure of compliance, we will evaluate the concentration of serum TXB2, a reliable marker of aspirin use.

The chemoprevention research nurse and the physicians will provide education for subjects, indicating when and how should the tablets be administered (general measures to reduce risk of GI adverse effects).

In case of concomitant medications, subjects are asked to contact the chemoprevention staff in order to check whether any potential interference is expected. Data on drug suspension or interruption will be reported into the CRFs.

## 6. PHARMACEUTICAL INFORMATION

### 6.1 Study Agent (IND #, IND Sponsor)

FDA has determined that the study is exempt from the IND requirement

### 6.2 Reported Adverse Events and Potential Risks

Potential risks and rare side effects related to the treatment can be summarized in the following four major categories:

- Upset stomach and heartburn.
- Easy bruising/bleeding, difficulty hearing, ringing in the ears, change in the amount of urine, persistent or severe nausea/vomiting, unexplained tiredness, dizziness, dark urine, yellowing eyes/skin.
- Black/tarry stools, persistent or severe stomach/abdominal pain, vomit that looks like coffee grounds, slurred speech, weakness on one side of the body, sudden vision changes or severe headache.
- Rash, itching/swelling (especially of the face/tongue/throat), severe dizziness, trouble breathing.

## 6.3 Availability

Bulk aspirin and matching placebo will be manufactured and supplied by Bayer Europe, using a dose currently available on the European market. Packaging and labeling will be performed by Monteresearch srl, Bollate, Italy and labeling performed by MRIGlobal for US supplies.

Aspirin is provided to the EIO under a Clinical Trials Agreement (CTA) between Bayer Europe and the EIO (see §12.7).

## 6.4 Agent Distribution

Agents will only be released by NCI, DCP after documentation of IRB approval of the DCP-approved protocol and consent is provided to DCP and the collection of all Essential Documents is complete (see DCP website for description of Essential Documents).

### *EIO*

Bayer Europe will release active drug and matching placebo to the EIO only after documentation of IRB approval and a specific contract has been signed by the EIO representative. The distributor will be Bayer Europe.

Bayer will ship the unmasked drug to the external Pharmacy service appointed by the EIO (Monteresearch srl, Bollate, Italy) that will be responsible for re-labeling and packaging the bottles according to protocol requirements. Each bottle contains 30 tablets. The pharmacy service will provide blinded study agent to investigators with a current FDA form 1572 filed with DCP. Drug will not be used or distributed out of the present protocol.

### MD Anderson

For US clinical supplies, the packaged drug will be labeled in US English by the NCI DCP repository, MRIGlobal. The NCI DCP repository will distribute the clinical material to MDACC.

NCI, DCP-supplied agents may be requested by the Investigator (or their authorized designees) at each Organization. DCP guidelines require that the agent be shipped directly to the institution or site where the agent will be prepared and administered. DCP does not permit the transfer of agents between institutions (unless prior approval from DCP is obtained). DCP does not automatically ship agents; the site must make a request. Agents are requested by completing the DCP Clinical Drug Request form (NIH-986) (to include complete shipping contact information) and faxing or mailing the form to the DCP agent repository contractor:

[name]  
MRIGlobal  
DCP Repository  
[name]  
[name]  
[contact]  
[contact]  
Emergency [contact]

## 6.5 Agent Accountability

The Investigator, or a responsible party designated by the Investigator, must maintain a careful record of the inventory and disposition of all agents received from DCP using the NCI Drug Accountability Record Form (DARF) or an institutionally-approved accountability system. The Investigator is required to maintain adequate records of receipt, dispensing and final disposition of study agent. Include on receipt record from whom the agent was received and to whom study agent was shipped, date, quantity and batch or lot number. On dispensing record, note quantities and dates study agent was dispensed to and returned by each participant. At EIO, this responsibility has been delegated to EIO Pharmacy. At MD Anderson, this responsibility has been delegated to MDACC Investigational Pharmacy.

## 6.6 Packaging and Labeling

Aspirin and matching placebo will be provided to EIO by Bayer Europe as a bulk shipment, but labeled and packaged by an external Pharmacy where they will be stored until delivery. An undisclosed randomization list will be provided by the statistician to the dedicated Pharmacist. Each package consists of a 7-month supply of the drug or placebo. Each box contains seven bottles with 30 tablets each. Each box will be labeled with the following information: EIO study number (S-XXX), randomization number (3 digits), PI's name and phone number, number of total doses, daily dose and schedule, lot numbers and expiring dates, specific instruction such as storage temperature, indication to keep the bottle out of reach of children. Subject's identification number will not be reported on drug packages. The same instructions will be stuck in the external part of the box package. Half of the label will be removed from the box and stuck into the drug delivery CRF to confirm appropriate drug has been administered to the subject.

For clinical supplies in the US, the NCI, DCP repository (MRIGlobal) will perform the product labeling, using US English labels, and will store the product for distribution to MDACC.

## 6.7 Storage

Study drug will be stored in a secure location, at controlled room temperature (59°F and 86°F) under low humidity.

## 6.8 Registration/Randomization

### *Baseline/ Registration into the DMI Database:*

Participants will be screened, consented and, once informed consent has been signed, participants will be registered into the DMI database. The DMI database will assign a participant's PID upon completion of the registration process.

